9.7.7 Health Economics and Outcomes Research Analyses

Not applicable.

9.7.8 Interim Analysis

No interim analysis is planned for this study.

9.7.9 Determination of Sample Size

This is a long-term open-label study of the safety and tolerability of vilazodone in pediatric patients with MDD. *To allow for all patients who complete the short-term lead-in study (VLZ-MD-22) to have the option to roll over into this extension study if eligible*

9.7.10 Computer Methods

9.8 CHANGES IN THE CONDUCT OF THE STUDY OR PLANNED ANALYSES

Any amendment to this protocol will be provided to the Investigator in writing by FRI. No protocol amendment may be implemented (with the exceptions noted below) before it has been approved by the IRB/IEC and the signature page, signed by the Investigator, has been received by FRI. If the protocol is amended to eliminate or reduce the risk to patients, the amendment may be implemented before IRB/IEC review and approval. However, the IRB/IEC must be informed in writing of such an amendment, and approval must be obtained within reasonable time limits.

9.9 PROTOCOL DEVIATIONS

A *protocol deviation* is any change, divergence, or departure from the study design or procedures that is under the Investigator's responsibility and oversight (as defined by regulations) without prior written IRB/IEC approval or favorable opinion of an appropriate amendment and that does not have a major impact on the patient's rights, safety, or well-being, or on the integrity and authenticity of the study data. Deviations may include, but are not limited to:

- Departure from inclusion/exclusion criteria
- Taking prohibited medications
- Departure from prescribed dosing or duration of treatment
- Failure to follow withdrawal criteria
- Failure to perform the required assessments at specified time points
- Scheduling of visits not in accordance with protocol specifications

Deviating from the protocol is permitted only if absolutely necessary for the safety or clinical management of the patients and must immediately be reported to FRI. Protocol deviations should be reported to FRI (either verbally or electronically) in a timely manner from the date of discovery.

Protocol deviations that may impact patients' rights (eg, failure to obtain informed consent prior to initiating study procedures), safety, or well-being (eg, deviations that resulted in an SAE, exposure during pregnancy), or the integrity and authenticity of the study data should be reported to FRI within 24 hours, if possible.

The IRB/IEC must be notified according to the criteria and time period dictated by the IRB/IEC associated with this study.

9.10 DATA MONITORING COMMITTEE

An independent Data Monitoring Committee to evaluate safety study outcomes such as suicidal ideation and suicidal behavior during study conduct will be established and will operate based on a charter drafted to comply with FDA Guidance for Clinical Trial Sponsors: Establishment and Operation of Clinical Trial Data Monitoring Committees, 2006.

10.0 STUDY SPONSORSHIP

This study is sponsored by Forest Research Institute, Inc.

[figure not shown]
[figure not shown]
10.1 STUDY TERMINATION

[figure not shown]
[figure not shown]
FRI reserves the right to terminate the study in its entirety or at a specific study center before study completion.

10.2 REPORTING AND PUBLICATION

All data generated in this study are the property of FRI. An integrated clinical and statistical report will be prepared at the completion of the study.

Publication of the results by the Investigator will be subject to mutual agreement between the Investigator and FRI and will follow FRI's standard operating procedures on publications.

11.0 INVESTIGATOR OBLIGATIONS**11.1 DOCUMENTATION**A large black rectangular redaction box covers the majority of the page content below the 11.1 section header, starting from the bottom of the header and extending down to the 11.2 section header.**11.2 PERFORMANCE**A large black rectangular redaction box covers the majority of the page content below the 11.2 section header, starting from the bottom of the header and extending down to the bottom of the page.

11.3**USE OF INVESTIGATIONAL MATERIALS**A large black rectangular redaction box covering the majority of the page content below the section header.**11.4****CASE REPORT FORMS**A large black rectangular redaction box covering the majority of the page content below the section header.**11.5****RETENTION AND REVIEW OF RECORDS**

Records and documents pertaining to the conduct of this study, including eCRFs, source documents, consent forms, regulatory documents, clinical laboratory results, calibration logs, or reports (including, but not limited to, all local and central laboratory results and ECG reports), and medication inventory records in all formats (including, but not limited to, written, electronic, magnetic, and optical records, and scans, x-rays, and ECGs) must be retained by the Investigator for a period of at least 15 years after study completion unless local regulations or institutional policies require a longer retention period or otherwise notified in writing by FRI.

[figure not shown]
No study records shall be destroyed without notifying FRI and providing FRI the opportunity to arrange long-term storage for such study records or authorizing in writing the destruction of records after the required retention period.

The Investigator must permit access to any documentation relating to the study upon request of FRI or applicable regulatory authorities. If the Investigator for the study retires, relocates, or for other reasons withdraws from the responsibility of keeping the study records, custody must be transferred to a suitable alternate custodian employee of the institution or to a suitably qualified and responsible third party. FRI must be notified in writing of the name and address of the new custodian in advance of the transfer.

For Canadian study centers only: All records and documents pertaining to the conduct of the study must be retained for a 25-year period in accordance with the Canadian Food and Drugs Act and Regulations.

11.6 PATIENT CONFIDENTIALITY

All patient records will only be identified by initials and PID number. Patients' names are not to be transmitted to FRI. The Investigator will keep a master patient list on which the PID number and the full name, address, and telephone number of each patient are listed.

12.0**INVESTIGATOR'S STATEMENT**

13.0**APPENDICES****APPENDIX I. ELEMENTS OF INFORMED CONSENT**

Procedures will comply with 21 CFR, Parts 50 and 312. Signed informed consent will be obtained for each patient participating in a clinical research study or from the patient's parent/guardian/LAR. This consent must include the following items:

- A statement that the study involves research and an explanation of the purposes of the research; a description of the procedures to be followed and the identification of any procedures that are experimental; and the expected duration of the patient's participation
- A description of any reasonably foreseeable risks or discomforts to the patient
- A description of any benefits to the patient or to others that may reasonably be expected from the research. If the patient is to be paid for participating in the study, the consent form must state the amount that he/she will receive and the schedule of payment (to ensure neither coercion nor undue influence)
- A disclosure of appropriate alternative procedures or courses of treatment, if any, that might be advantageous to the patient
- A statement describing the extent, if any, to which confidentiality of records identifying the patient will be maintained and noting the possibility that the FDA; FRI, the IRB; or an authorized contract research organization may inspect the records
- For research involving more than minimal risk, an explanation of whether any medical treatment is available if injury occurs and, if so, what it consists of or where further information may be obtained
- An explanation of whom to contact, including the relevant telephone number, for answers to pertinent questions about the research and the research patient's rights and whom to contact in the event of a research-related injury to the patient. (Note: In some cases, it may be necessary to identify a person other than the Investigator as the contact. The guidance of the IRB/EC may be required)
- A statement that participation is voluntary, that refusal to participate will involve no penalty or loss of benefits to which the patient is otherwise entitled, and that the patient may discontinue participation at any time without penalty or loss of benefits to which the patient is otherwise entitled

- A statement that the particular treatment or procedures may involve risks to the patient (or to the embryo or fetus if the patient is, or may become, pregnant) that are at present unforeseeable
- The expected circumstances for which the patient's participation may be terminated by the Investigator without regard to the patient's consent
- Any additional costs to the patient that may result from participation in the research
- The consequences of a patient's decision to withdraw from the research and procedures for an orderly termination of the patient's participation
- A statement that significant new findings developed during the course of the research that may relate to the patient's willingness to continue participation will be provided to the patient
- The approximate number of patients involved in the study
- A statement of permission, providing consent for the patient to participate (eg, "I agree to allow (my child) to participate . . .")
- A place for the patient's parent/guardian/LAR signature and date of signing of the ICF
- A statement indicating that information about this study has been, or will be, entered into a databank that is publicly accessible at www.ClinicalTrials.gov.

[figure not shown]
A copy of the signed consent form must be given to the patient's parent/guardian/LAR.

[figure not shown]
In addition, the patient will be asked to provide assent that will include a statement agreeing to participate in the study.

[figure not shown]

APPENDIX III. CONCOMITANT MEDICATIONS

[figure not shown]

[figure not shown]

[figure not shown]

[figure not shown]
APPENDIX IV. CHILDREN'S DEPRESSION RATING SCALE-REVISED

[figure not shown]

[figure not shown]

APPENDIX V. CLINICAL GLOBAL IMPRESSIONS-SEVERITY

**APPENDIX VI. CLINICAL GLOBAL IMPRESSIONS—IMPROVEMENT
GLOBAL IMPROVEMENT**

APPENDIX VII. COLUMBIA–SUICIDE SEVERITY RATING SCALE - BASELINE**COLUMBIA–SUICIDE SEVERITY
RATING SCALE
(C-SSRS)**Baseline
Version 1/14/09

Posner, K.; Brent, D.; Lucas, C.; Gould, M.; Stanley, B.; Brown, G.; Fisher, P.; Zelazny, J.; Burke, A.; Oquendo, M.; Mann, J.

[figure not shown]
Disclaimer:

[figure not shown]
This scale is intended for use by trained clinicians. The questions contained in the Columbia–Suicide Severity Rating Scale are suggested probes. Ultimately, the determination of the presence of suicidality depends on clinical judgment.

[figure not shown]
Definitions of behavioral suicidal events in this scale are based on those used in The Columbia Suicide History Form, developed by [name] and [name], Conte Center for the Neuroscience of Mental Disorders (CCNMD), New York State Psychiatric Institute, [name]. (Oquendo M. A., Halberstam B. & Mann J. J., Risk factors for suicidal behavior: utility and limitations of research instruments. In M.B. First [Ed.] Standardized Evaluation in Clinical Practice, pp. 103 -130, 2003.)

For reprints of the C-SSRS contact [name]., New York State Psychiatric Institute, [name]; inquiries and training requirements contact [contact]

© 2008 The Research Foundation for Mental Hygiene, Inc.

APPENDIX VIII. COLUMBIA–SUICIDE SEVERITY RATING SCALE - SINCE LAST VISIT**COLUMBIA–SUICIDE SEVERITY
RATING SCALE
(C-SSRS)**
Since Last Visit
Version 1/14/09

Posner, K.; Brent, D.; Lucas, C.; Gould, M.; Stanley, B.; Brown, G.; Fisher, P.; Zelazny, J.; Burke, A.; Oquendo, M.; Mann, J.

[figure not shown]
Disclaimer:

[figure not shown]
This scale is intended for use by trained clinicians. The questions contained in the Columbia–Suicide Severity Rating Scale are suggested probes. Ultimately, the determination of the presence of suicidality depends on clinical judgment.

[figure not shown]
Definitions of behavioral suicidal events in this scale are based on those used in The Columbia Suicide History Form, developed by [name] and [name], Conte Center for the Neuroscience of Mental Disorders (CCNMD), New York State Psychiatric Institute, [name]. (Oquendo M. A., Halberstam B. & Mann J. J., Risk factors for suicidal behavior: utility and limitations of research instruments. In M.B. First [Ed.] Standardized Evaluation in Clinical Practice, pp. 103 -130, 2003.)

APPENDIX IX. INVESTIGATIONAL PRODUCT FORMULATION

- Ingredients of vilazodone [REDACTED]

2.1 LIST OF IN-TEXT TABLES

Table 4–1.	SCHEDULE OF EVALUATIONS: Study VLZ-MD-23	7
Table 11.2–1.	Criteria for Potentially Clinically Significant Laboratory Values	18
Table 11.3–1.	Criteria for Potentially Clinically Significant Vital Signs	20
Table 11.4–1.	Criteria for Potentially Clinically Significant Electrocardiographic Parameters	22
Table 16.1–1.	Visit Time Windows for the Open-Label Treatment Period	28
Table 16.1–2.	Visit Time Windows for the Open-label Down-Taper Period.....	29
Table 16.10–1.	Examples of Coding Special Character Values for Clinical Laboratory Parameters	35
Table 19–1.	List of Selected Parameters Reported in Conventional Unit	38
Table 19–2.	Presenting Laboratory Data Using SI and Conventional Units in Narratives	39

3.0

LIST OF ABBREVIATIONS

AE	adverse event
ALT	alanine aminotransferase
AST	aspartate aminotransferase
ALP	alanine phosphatase
BP	blood pressure
CDR-S	Children's Depression Rating Scale-Revised
CGI-I	Clinical Global Impression-Improvement
CGI-S	Clinical Global Impression-Severity
C-SSRS	Columbia Suicide Severity Rating Scale
ECG	Electrocardiogram
ITT	Intent-to-Treat
LLN	lower limit of normal
LOCF	last observation carried forward
MedDRA	Medical Dictionary for Regulatory Activities
NEAE	newly emergent adverse event
PCS	potentially clinically significant
SAE	serious adverse event
SAP	Statistical Analysis Plan
SI	Le Système International d'Unités (International System of Units)
SOC	system organ class
TBL	total bilirubin
TEAE	treatment emergent adverse event
ULN	upper limit of normal

4.0

INTRODUCTION

This statistical analysis plan (SAP) provides a more technical and detailed elaboration of the statistical analyses of the efficacy and safety data as outlined and/or specified in the protocol of Study VLZ-MD-23. Specifications of tables, figures, and data listings are contained in a separate document. The statistical analysis for pharmacokinetic parameters will be specified in a separate document.

Study VLZ-MD-23 will be an open-label, long-term safety study in pediatric patients, ages 7 to 17 years with major depressive disorder (MDD). Eligible patients will include de novo patients meeting the inclusion/exclusion criteria and patients who completed the lead-in study (VLZ-MD-22). Study centers will enroll either de novo patients or patients who completed the lead in study. Patients who complete Study VLZ-MD-22 will have the option to participate in Study VLZ-MD-23.

[figure not shown]
The study will be approximately 28 weeks in duration, including approximately a 1-week screening/washout period, a 26-week open-label treatment period, and a 1-week down-taper period. During the open-label treatment period, study visits will be conducted after 2, 3, 4, 6, 8, 10, 12, 14, 16, 18, 20, 22, 24, and 26 weeks of treatment (see [Table 4-1](#)). Safety and efficacy assessments will be performed at the designated visits. Patients prematurely discontinuing from the study, regardless of cause, will be seen for a final evaluation.

This statistical analysis plan (SAP) provides a more technical and detailed elaboration of the statistical analyses for efficacy and safety assessments as outlined and/or specified in the final study protocol (version dated 15 Dec 2014). Specifications of tables, figures, and data listings are contained in a separate document.

Table 4–1. SCHEDULE OF EVALUATIONS: Study VLZ-MD-23

Table 4-1.

SCHEDULE OF EVALUATIONS: Study VLZ-MD-23

The table content is completely obscured by a large black rectangular redaction box.

5.0**OBJECTIVE**

The objective of this study is to evaluate the long-term safety and tolerability of vilazodone for the treatment of MDD in pediatric outpatients (7-17 years).

6.0 PATIENT POPULATIONS

Four populations will be considered in the statistical analysis of the study, as specified below.

6.1 SCREENED POPULATION

The Screened Population will consist of all patients who signed informed consent for this study.

6.2 ENROLLED POPULATION

The Enrolled Population will consist of all patients in the Screened Population who were dispensed investigational product.

6.3 SAFETY POPULATION

The Safety Population will consist of all patients who took at least 1 dose of open-label investigational product.

6.4 INTENT-TO-TREAT POPULATION

The Intent-to-Treat (ITT) Population will consist of all patients in the Safety Population who had a baseline and at least 1 postbaseline assessment of the Children's Depression Rating Scale-Revised (CDRS-R) total score.

7.0

PATIENT DISPOSITION

The number of patients in the Screened Population will be summarized overall by study center. The number of patients in the Enrolled, Safety, and ITT populations will be summarized by study center.

Screen failures (ie, patients who were screened but not included in the Enrolled Population) and the associated reasons for failure will be tabulated. The number and percentage of patients who complete the open-label treatment period and of patients who prematurely discontinue during the same period will be presented. The reasons for premature discontinuation from the open-label treatment period as recorded on the disposition pages of the electronic case report forms will be summarized (number and percentage) for the Safety Population. All patients who prematurely discontinue during the open-label treatment period will be listed by discontinuation reason for the Safety Population.

All summaries in this section will be presented by patient cohort (rollover patients from Study VLZ-MD-22 or *de novo* patients) and overall. The rollover patients from Study VLZ-MD-22 will be summarized by lead-in treatment group.

8.0

DEMOGRAPHICS AND OTHER BASELINE CHARACTERISTICS

[figure not shown]
Demographic parameters (age, sex, race, ethnicity) and other baseline characteristics (weight, height, body mass index) will be summarized descriptively by cohort and by lead-in treatment group for the Safety and ITT populations, respectively. Baseline efficacy variables will be summarized by cohort and by lead-in treatment group for the ITT Population.

Continuous variables will be summarized by number of patients and mean, SD, median, minimum, and maximum values. Categorical variables will be summarized by number and percentage of patients.

Medical and surgical history/physical findings will be classified by system organ class (SOC) and preferred term using the *Medical Dictionary for Regulatory Activities*, version 17.0 or newer. The number and percentage of patients with abnormalities in medical and surgical histories in each SOC and preferred term will be summarized by cohort and by lead-in treatment group for the Safety Population. Psychiatric history of MDD, other psychiatric history, prior treatment with psychotropic medication, and non-drug psychiatric treatment history will also be summarized by cohort and by lead-in treatment group for the Safety Population.

[figure not shown]
The *World Health Organization Drug Dictionary*, version March 2014 or newer, will be used to classify prior and concomitant medications by therapeutic class and drug name.

Prior medication is defined as any recorded medication taken before the date of the first dose of open-label investigational product. *Concomitant medication* is defined as any medication taken on or after the date of the first dose of open-label investigational product.

9.0**EXTENT OF EXPOSURE AND TREATMENT COMPLIANCE****9.1****EXTENT OF EXPOSURE**

Exposure to open-label investigational product for the Safety Population during the open-label treatment period will be summarized in terms of treatment duration, calculated as the number of days from the date of the first dose of open-label investigational product to taken the date of the last dose of open-label investigational product taken during the open-label treatment period, inclusive. Descriptive statistics (number of patients, mean, SD, median, minimum, and maximum) will be presented by cohort and by lead-in treatment group. The number and percentage of patients by exposure will be presented for specific intervals by cohort.

**9.2****MEASUREMENT OF TREATMENT COMPLIANCE**

10.0

EFFICACY ANALYSES

All efficacy analyses will be based on the ITT Population. For patients who completed the lead-in study (VLZ-MD-22), the baseline for efficacy from the lead-in study will be used as the baseline for this study. For de novo patients, the latest nonmissing evaluation of efficacy variables (at or prior to Visit 2) before the first dose of open-label investigational product will be used as baseline. Descriptive statistics for each efficacy parameter (n, mean, SD, SEM, median, minimum, and maximum) will be presented for each visit, by cohort and by lead-in treatment group for continuous variables using observed case (OC) approach. At a specific visit, only patients in the ITT Population with both baseline and post-baseline values will be included in the summary.

In addition, by-visit analyses using the last-observation-carried-forward (LOCF) approach will be presented for each efficacy parameters. For the LOCF approach, only the postbaseline total score of a parameter will be imputed; individual item scores will not be carried forward to derive the total score. Baseline total score will be carried forward only for the intermittent missing scores immediately after baseline. If all the postbaseline values are missing, the baseline value will not be carried forward.

The efficacy parameters will include the following at selected postbaseline visits:

- Change from baseline in CDRS-R total score
- Change from baseline in Clinical Global Impressions – Severity (CGI-S) score
- Clinical Global Impressions – Improvement (CGI-I) score

11.0 SAFETY ANALYSES

The safety analysis will be performed for the open-label treatment period and down-taper period separately using the Safety Population. The safety analyses will be presented by patient cohort (rollover patients from Study VLZ-MD-22 and *de novo* patients) and overall. The rollover patients from Study VLZ-MD-22 will also be presented by lead-in treatment group.

The safety parameters will include adverse events (AEs), clinical laboratory parameters, vital sign measurements, electrocardiogram (ECG) parameters, Columbia Suicide Severity Rating Scale (C-SSRS) evaluations, and the change from baseline in the age- and gender-adjusted height (evaluation of growth). For patients who completed the lead-in study (VLZ-MD-22), the baseline for safety parameters from the lead-in study will be used as the baseline for this study. For *de novo* patients, the latest nonmissing evaluation of safety parameters before the first dose of open-label investigational product will be used as the baseline.

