9.1.1 Screening Period

[figure not shown]
Patients who completed lead-in study VLZ-MD-22 will have completed a down-taper period at the end of study VLZ-MD-22 and will not be required to undergo a washout period.

For de novo patients, the screening/washout period will generally be 1 week prior to Visit 2 (Baseline), but may be extended up to a total of 5 weeks to accommodate prior medication washout or repeat assessments (with prior approval of the Study Physician or designee). At the end of Visit 2 (Baseline), patients who meet the eligibility criteria will be enrolled into the study.

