9.7.6 Safety Analyses

The safety analysis will be performed for the open-label treatment period and down-taper period separately using the Safety Population. The safety analyses will be presented by patient cohort (rollover patients from Study VLZ-MD-22 and *de novo* patients) and overall.

The safety parameters will include AEs, clinical laboratory parameters, vital sign measurements, ECG parameters, C-SSRS evaluations, and the change from baseline in the age- and gender-adjusted height (evaluation of growth). For patients who completed the lead-in study (VLZ-MD-22), the baseline for safety from the lead-in study will be used as the baseline for this study. For *de novo* patients, the latest nonmissing evaluation of safety variables before the first dose of open-label investigational product will be used as baseline.

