11.3 VITAL SIGNS

[figure not shown]
Descriptive statistics for vital signs (ie, sitting radial pulse rate, sitting systolic and diastolic blood pressure (BP), body weight, and height) and changes from baseline values at each visit and at the end of the open-label treatment period will be presented. In addition, height and weight z scores will be calculated based on growth charts.

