16.4 REPEATED OR UNSCHEDULED ASSESSMENTS OF SAFETY PARAMETERS

For roll-over patients, the corresponding baseline of the double-blind lead-in study will be used. If a de novo patient has repeated assessments before the date of the first dose of open-label investigational product, the results from the final nonmissing assessment made before the date of the first dose of open-label investigational product will be used as baseline. If the end-of-open-label-treatment period assessments are repeated or if unscheduled visits occur, the last nonmissing postbaseline assessment during the open-label treatment period will be used as the end-of-open-label-treatment-period assessment for generating summary statistics. Likewise, if the end of open-label down-taper period assessments are repeated or if unscheduled visits occur, the last non-missing assessment during the open-label down-taper period will be used as the end-of-open-label-down-taper-period assessment for generating summary statistics. However, all postbaseline assessments will be used to determine PCS values for laboratory parameters, vital signs and ECG parameters, and to determine most severe suicidal ideation and most severe suicidal behavior from C-SSRS. All assessments will be presented in the data listings.

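### Rollover labs, vital signs, ECG/QTc and growth are visibly summarised only from the lead-in baseline, so the open-label tables mix lead-in change with open-label change

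*SAP*

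**What the plan says.** Three places fix the rollover reference without qualification. SAP 11.0: "the baseline for safety parameters from the lead-in study will be used as the baseline for this study". Protocol 9.7.6: "the baseline for safety from the lead-in study will be used as the baseline for this study". SAP 16.4: "For roll-over patients, the corresponding baseline of the double-blind lead-in study will be used". For de novo patients SAP 11.0 instead takes the value just before open-label dosing: "the latest nonmissing evaluation of safety parameters before the first dose of open-label investigational product will be used as the baseline".

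These baselines feed the following summaries:

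- Change from baseline for laboratory values (SAP 11.2), vital signs (SAP 11.3: "changes from baseline values at each visit and at the end of the open-label treatment period will be presented"), ECG parameters (SAP 11.4), and raw and age- and sex-adjusted height and weight (SAP 11.5.2).
- PCS rates. For labs and ECG, the denominator is patients who were not PCS at baseline (Protocol 9.7.6.2, 9.7.6.4). For vital signs, change from baseline is part of the PCS definition (Protocol 9.7.6.3).
- QTc increases of more than 30 and up to 60 msec, and of more than 60 msec (Protocol 9.7.6.4).

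SAP 11.0 states that the safety analysis covers the open-label and down-taper periods separately. It is shown by cohort and overall, with rollovers also split by lead-in treatment group.

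Adverse events are handled differently. SAP 11.1 counts treatment-emergent events in rollovers from the first double-blind dose. It then adds newly emergent events (NEAEs), judged against the first open-label dose.

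**The concern.** The sole objective is long-term safety and tolerability. Rollovers arrive from a placebo- and active-controlled trial of vilazodone (Protocol 14.0, entry for VLZ-MD-22). A table labelled as open-label but measured from the lead-in baseline cannot show whether a laboratory, vital-sign, QTc or growth change began before or after the first open-label dose. Splitting rollovers by lead-in treatment shows where patients came from but does not subtract what happened there.

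The SAP already recognises the need for AEs, through the NEAE definition. Without the same step for measured parameters, a reader has a rate of new AEs on open-label drug but no matching rate for PCS values or QTc increases.

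**Working it through.** The plan states no figure to reproduce. The check is a reading of the rules, followed by illustrations on assumed values.

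**1. References side by side (rollovers).**

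| Item | Reference in readable text |
|---|---|
| Treatment-emergent AEs | first double-blind dose (SAP 11.1) |
| Newly emergent AEs | first open-label dose (SAP 11.1) |
| Open-label exposure | first open-label dose (SAP 9.1) |
| Labs, vital signs, ECG/QTc, growth | lead-in baseline only (SAP 11.0, 16.4; Protocol 9.7.6) |

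The documents do not define the lead-in baseline further. That it precedes lead-in drug is inferred, and agrees with the treatment-emergent AE rule.

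**2. Identity.** Planned change = lead-in change + open-label change.

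**3. QTcF against the protocol's 30 msec cut** (invented values: lead-in entry, before open-label, on open-label).

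- 400, 420, 433: planned change 433 - 400 = 33, counted; open-label change 433 - 420 = 13.
- 420, 395, 430: planned change 430 - 420 = 10, not counted; open-label change 430 - 395 = 35.

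**4. Effect of a mean lead-in shift on the QTc rate.** Assume normal changes, a true mean open-label change of 0, and SD 15 msec for either baseline. With mean lead-in shift d, P(increase > 30) = 1 - Φ((30 - d)/15).

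- d = -10: 1 - Φ(2.67) = 0.4%
- d = 0, which is also the open-label-baseline result: 1 - Φ(2) = 2.3%
- d = +10: 1 - Φ(1.33) = 9.1%

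With SD 12 the range is 0.04% to 4.8% (open-label baseline 0.6%). With SD 20 it is 2.3% to 15.9% (open-label baseline 6.7%).

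**5. PCS counts for one lab or ECG parameter, overall column.** N = 315 is from Protocol 9.1.2; every rate is assumed. Rollovers are 25% to 75% of patients: 315 × 0.25 = 78.75 to 315 × 0.75 = 236.25.

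- Additions are lead-in PCS values that persist, counting only patients from placebo or active control (33% to 67% of rollovers, 0.5% to 2% of these). Lowest: 78.75 × 0.33 × 0.005 = 0.13. Highest: 236.25 × 0.67 × 0.02 = 3.17.
- Removals are patients PCS at lead-in entry (1% to 5% of rollovers) who normalise and become PCS again on open-label drug (5% to 20% of these). They leave both numerator and denominator. Lowest: 78.75 × 0.01 × 0.05 = 0.04. Highest: 236.25 × 0.05 × 0.20 = 2.36.
- Net at 75% rollovers, lowest: 236.25 × 0.33 × 0.005 - 2.36 = 0.39 - 2.36 = -1.97 (-0.63% of 315).
- Net at 75% rollovers, highest: 3.17 - 236.25 × 0.01 × 0.05 = 3.17 - 0.12 = +3.05 (+0.97%).
- Net at 25% rollovers: -0.66 to +1.02 patients. With the 250 patients in SAP 14.0 and 75% rollovers: -1.57 to +2.42.

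The sign is open.

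**6. Growth.** Lead-in length is not readable. If it is 4, 8 or 12 weeks, the share of the span to Week 26 that precedes open-label dosing is 4/30 = 13%, 8/34 = 24% or 12/38 = 32%, ignoring taper and gaps. No growth effect is estimated.

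**The case against.** The strongest reply is that the lead-in baseline is deliberate, consistent across both documents, and the natural reference for cumulative safety in a purely descriptive study. It also puts both cohorts on a pre-drug footing: de novo patients before open-label drug, rollovers before lead-in drug. That stands. It is why the lead-in baseline should remain the main one, and why the second baseline should not get a pooled overall column. Such a column would mix pre-drug de novo values with rollover values taken after placebo, active control or vilazodone. Rollovers "will have completed a down-taper period at the end of study VLZ-MD-22 and will not be required to undergo a washout period", so the later value may carry residual or discontinuation effects. The second QTcF example in the working shows the same limit: its 35 msec rise starts from a dip and may be a return toward the usual value.

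Mitigations also stand in part:

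- The de novo cohort is shown separately, and rollovers are split by lead-in group.
- Observed values are summarised by time point, and SAP 16.4 says "All assessments will be presented in the data listings".
- Protocol 9.5.2.1 treats clinically relevant laboratory and physical findings as AEs, so these reach the NEAE rates once reported.
- Inclusion criterion 7 limits clinically significant abnormality at entry.

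None of these yields a within-patient open-label change, a PCS rate or a QTc category measured from the first open-label dose.

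Two stronger readings are tempting. First, because SAP 16.4 says that "all postbaseline assessments will be used to determine PCS values for laboratory parameters, vital signs and ECG parameters", a reader might infer that lead-in PCS values themselves count as open-label events. SAP 11.0 separates the study periods, so the text does not support that; a clarifying clause is enough. Second, a reader might infer that open-label suicidality cannot be separated from the lead-in. It can: the C-SSRS asks about the time since the previous visit (Protocol 9.5.2.12.2) and SAP 11.5.1 reports by period. The narrower gap is that rollover lifetime history is copied from lead-in Visit 1, so events during the lead-in fall in none of the summarised periods.

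**Conclusion.** This is a cheap improvement, not an error. In the readable text, rollover laboratory, vital-sign, ECG/QTc and growth tables for the open-label period combine two phases of change, and no summary isolates the second.

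A reader might infer that the plan inflates or hides open-label signals. The documents support neither: the effect can run either way, and lead-in length, arm sizes and rollover share are not readable. The -0.6 to +1.0 percentage point range and the QTc tail rates rest entirely on assumed inputs and are illustrations, not estimates.

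Confidence is moderate. SAP 11.2 to 11.4 are partly unreadable, and SAP 4.0 places table specifications in a separate document. If either already defines a second rollover baseline, the point falls away.

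**What to change.** Keep the lead-in baseline as the main reference and add to SAP 11.0:

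> For rollover patients, supplementary change-from-baseline, PCS, QTc-increase and z-score-change tables for the open-label treatment period will be presented by lead-in treatment group. Their baseline is the last nonmissing value before the first open-label dose, with its source (entry to this study or the lead-in study) flagged. They are to be read beside the lead-in-baseline tables, because this baseline follows lead-in treatment and down-taper. Postbaseline assessments in them are those after the first open-label dose.

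Do not add a pooled overall column on this baseline. The AE tables need no change. If a second baseline already exists in the table specifications, state it in SAP 11.0 instead.

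**Cost.** One baseline flag, one source flag and an extra set of descriptive tables. The new baseline may carry residual lead-in drug or discontinuation effects, most of all in patients who received vilazodone in the lead-in, so it supplements the existing one. Patients already PCS at the new baseline would leave the new lab and ECG rates, if the same denominator rule is used.

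**Data availability is inferred.** Protocol 9.3.1 treats only criteria 2 to 5 as already met for rollovers. Criterion 7 therefore still applies and implies entry labs, vital signs and ECG, but the visit procedures are not readable. Where there is no entry value, the last lead-in value would serve, hence the source flag.

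**Optional and separate.** A C-SSRS shift table for rollovers that includes the lead-in since-last-visit records, to show new or worse categories in the open-label period.
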